7.1.4 Serious Adverse Events

A serious adverse event (SAE) is defined as any untoward medical occurrence that at any dose results in one or more of the following:

- Death.
- Is life-threatening (i.e., the subject was, in the opinion of the investigator, at immediate risk of death from the event as it occurred); it does not refer to an event which hypothetically might have caused death if it were more severe.
- Required or prolonged hospitalization.
- Persistent or significant disability/incapacity (i.e., the event causes a substantial disruption of a person's ability to conduct normal life functions).
- Congenital anomaly/or birth defect.
- An important and significant medical event that may not be immediately life threatening or resulting in death or hospitalization but, based upon appropriate medical judgment, may jeopardize the subject or may require intervention to prevent one of the other outcomes listed above.

Adverse events which do not fall into these categories are defined as non-serious.

It should be noted that a severe adverse event need not be serious in nature and that a serious adverse event need not, by definition, be severe.

Serious adverse events will be captured both on the Vaccines Serious Adverse Event (VSAE) form as well as on the AE CRF. All SAEs will be evaluated by the investigator for relationship of the event to study vaccine. SAEs that are judged to be possibly or probably related to the study vaccine should be reported to the Sponsor as related/suspected events.

The relationship of the study treatment to an SAE will be determined by the investigator based on the following definitions:

1. Related/suspected

The SAE is judged by the investigator to be possibly or probably related to the study vaccine on the AE CRF page (see [section 7.1.3, Evaluation of Adverse Events](#)).

2. Not Related

The SAE is not related if exposure to the study vaccine has not occurred, or the occurrence of the SAE is not reasonably related in time, or the SAE is considered unlikely to be related to use of the study vaccine, i.e., there are no facts (evidence) or arguments to suggest a causal relationship.

The relationship of the study vaccine to an SAE will be determined by the investigator.

In addition, SAEs will be evaluated by the Sponsor or designee for "expectedness." An unexpected AE is one that is not listed in the cUITent [Summary of Product Characteristics](#) or the Investigator's Brochure or an event that is by nature more specific or more severe than a listed event

In addition, a pre-existing event or condition that results in hospitalization should be recorded on the Medical History CRF. If the onset of an event occurred before the subject entered the study (e.g., any pre-planned hospitalization for conditions like cosmetic treatments or for non-emergency routine visits for a pre-existing condition), the hospitalization would not lead to an AE being classified as serious unless, in the view of the investigator, hospitalization was prolonged as a result of participation in the clinical study or was necessary due to a worsening of the pre-existing condition.

7.1.4.1 Adverse Events of Special Interest

Adverse Events of Special Interest (AESIs) will not be assessed during the study.

7.1.S Methods for Recording Adverse Events and Serious Adverse Events

Findings regarding Adverse Events must be reported on an Adverse Events CRF, as specified in [section 7.1.1, Solicited Adverse Events](#), and on the VSAE form, if applicable, which is part of the Investigator Site File. All findings in subjects experiencing AEs must be reported also in the subject's source document.

All SAEs which occur during the course of the study, whether considered to be associated with the study vaccination or not, must be reported within 24 hours of the site becoming aware of the event to GSK or its designee. Specific instructions and contact details for collecting and reporting SAEs to GSK will be provided to the investigator.

All SAEs are also to be documented on the Adverse Events CRF. Any medication or other therapeutic measures used to treat the AE will be recorded on the appropriate CRF(s) in addition to the outcome of the AE.

After receipt of the initial report, representatives of GSK or its designee will contact the investigator if it is necessary to obtain further information for assessment of the event.

All SAEs must be reported by the investigator to his/her corresponding EC/ IRB applicable regulatory authorities in accordance with institutional policy/regulatory requirements and adequate documentation of this notification must be provided to the Sponsor.

GSK or its designee must also comply with the applicable regulatory requirement(s) related to the reporting of suspected unexpected serious adverse vaccine reactions (also known as SUSARs) to the regulatory authority(ies) and the IRB/EC. If a SUSAR or other safety signal relating to use of one of the study vaccines is reported to GSK or its designee, the Sponsor will communicate the information to the investigator and the investigator will be responsible for submitting this information to the EC/IRB and other relevant authorities.

7.1.S.1 Post-Study Events

Any SAE that occurs outside of the protocol-specified follow-up period and considered to be caused by the study vaccine must be reported to GSK or its designee. These SAEs will be processed by GSK or its designee as during the course of the study, until 1 month after Last Subject Last Visit (LSLV). Instructions and contact details for collecting and reporting these suspected SAEs will be provided to the investigator.

7.16 Pregnancies

To ensure subjects' safety, each pregnancy in a subject after study vaccination must be reported to GSK or delegate within 72 hours of the site learning of its occurrence. If the subject agrees to submit this information, the pregnancy must be followed to determine outcome, including spontaneous or voluntary termination, details of the birth, and the presence or absence of any birth defects, congenital abnormalities, or maternal and/or newborn complications. This follow-up should occur even if intended duration of safety follow-up for the study has ended.

Pregnancy data must be recorded on a Pregnancy Report CRF (initial report) and Pregnancy Follow-Up CRF (outcome report) and reported to GSK or delegate. Instructions and contact details for submitting the Pregnancy CRFs will be provided to the investigator.

Any pregnancy outcome meeting the definition of a SAE (see [section 7.1.4, Serious Adverse Events](#)) must also be reported on the VSAE Report Form.

7.17 Safety Laboratory Measurements

No safety laboratory measurements will be done in this study.

7.2 Efficacy Assessment

This section is not applicable. This study has no efficacy measurements.

7.3 Immunogenicity Assessment

The functional measure of immunogenicity used in this study, Serum Bactericidal Assay (SBA), is a measure of the ability of antibodies, in concert with human complement, to kill meningococci, and is widely used and generally recognized as the serological correlate of protection. The key measures of immunogenicity will be the percentages of subjects with seroresponse¹¹, percentages of subjects who achieve hSBA titers 8 and, and the hSBA GMfs against serogroups A, C, W and Y reference strains.

These measurements will be assessed in serology samples collected at Visit Day 1, 4 or 8 and Day 29. The measures of immunogenicity used in this study are standard, i.e., widely

¹¹ Seroresponse to *N. meningitidis* serogroups A, C, W and Y is defined as: for subjects with a pre-vaccination hSBA titer < 4, a post-vaccination hSBA titer 2:8; for subjects with a pre-vaccination hSBA titer 2:4, an increase in hSBA titer of at least four times the pre-vaccination titer.

used and generally recognized as reliable, accurate, and relevant (able to describe the quality and extent of the immune response).

All subjects will have a blood draw at Day 1, before vaccination. Subsequent blood draws will be at either Day 4 or Day 6 post vaccination, and at Day 29 post vaccination.

Primary:

Collected samples may be used in other assays, for test improvement or development of analytical methods related to the study vaccines or the disease under evaluation to allow a more reliable measurement of the vaccine response. Under these circumstances, additional testing on the samples may be performed by GSK outside the scope of the protocol. Any sample testing will be done in line with the consent of the individual subject's parent/ guardian.

Testing will be conducted by qualified and certified laboratories. All assays will be performed in GSK, Clinical Laboratory Sciences, or a delegate laboratory.

8. STATISTICAL CONSIDERATIONS

8.1 Endpoints

8.1.1 Primary Endpoint(s)

8.1.1.1 Primary Safety Endpoint(s)

There are no primary safety endpoints in this study.

8.1.1.2 Primary Efficacy Endpoint(s)

There are no primary efficacy endpoints in this study.

8.1.1.3 Primary Immunogenicity Endpoint(s)

The following measure will be summarized for the pooled (Menveo-Menveo and Menactra-Menveo) group

1. Percentage of subjects with hSBA seroresponse⁵ against *N. meningitidis* serogroups A, C, W and Y at Day 29.

8.1.2 Secondary Endpoint(s)

8.1.2.1 Secondary Safety Endpoint(s)

Safety of the study vaccine will be assessed in the pooled vaccine group (Menveo-Menveo and Menactra-Menveo) and the vaccine-naive group in terms of the frequency (percentage) of reported adverse events including

1. Any unsolicited AEs reported within 30 minutes after vaccination;
2. Solicited local and systemic AEs reported from Day 1 (6 hours) through Day 7 after vaccination;
3. Other indicators of reactogenicity (e.g. use of analgesics/ antipyretics, body temperature) within 7 days after vaccination;
4. All unsolicited AEs reported from Day 1 through Day 29 after vaccination;

⁵ Seroresponse is defined as: a) post-vaccination hSBA ?:8 for subjects with a pre-vaccination hSBA <4; b) for subjects with a pre-vaccination hSBA ?:4, an increase of at least four times the pre-vaccination hSBA.

5. Medically-attended AEs, AEs leading to withdrawal and SAEs reported from Day 1 through Day 181 (entire study period).

Adverse events will be coded using MedDRA preferred terms as applicable.

8.1.2.2 Secondary Efficacy Endpoint(s)

There are no secondary efficacy endpoints in this study.

8.1.2.3 Secondary Immunogenicity Endpoint(s)

The following measures will be nmmari:1:ed for Menveo-Menveo, Menactra-Menveo, Naive and the pooled (Menveo-Menveo and Menactra-Menveo) groups unless otherwise noted:

1. Percentage of subjects with hSBA titer 8 against *N. meningitidis* serogroups A, C, W and Y at Day 1, Day 4, Day 6 and Day 29;
2. Percentages of subjects with hSBA seroresponse against *N. meningitidis* serogroups A, C, W and Y at Day 4, Day 6 and Day 29 (Day 29: Except the pooled group);
3. hSBA GMfs against *N. meningitidis* serogroup A, C, W and Y at Day 1, Day 4, Day 6 and Day 29;
4. Ratios of hSBA GMfs at Day 1, Day 4, Day 6 and Day 29 (between study groups).
5. Ratios of hSBA GMfs at Day 4, Day 6, and Day 29 compared to Day 1 (within study groups).

8.1.3 Exploratory Endpoint(s)

8.1.3.1 Exploratory Safety Endpoint(s)

There are no exploratory safety endpoints in this study.

8.1.3.2 Exploratory Efficacy Endpoint(s)

There are no exploratory efficacy endpoints in this study.

8.1.3.3 Exploratory Immunogenicity Endpoint(s)

There are no exploratory immunogenicity endpoints in this study.

8.2 Success Criteria

8.2.1 Success Criteria for Primary Objective(s)

8.2.1.1 Success Criteria for Primary Safety Objective(s)

There are no **primary** safety objectives in this study.

8.2.1.2 Success Criteria for Primary Efficacy Objective(s)

There are no **primary** efficacy objectives in this study.

8.2.1.3 Success Criteria for Primary Immunogenicity Objective(s)

To demonstrate immune response sufficiency after MenACWY-CRM booster vaccine administration, the lower limit of the one-sided 97.5% Confidence Interval(CI) for percentage of subjects with hSBA seroresponse against each of serogroups A, C, W and Y must be greater than 80% (in the pooled group of subjects who received **primary** vaccination with Menveo or Menactra). The threshold of 80% was previously agreed for demonstration of immune response adequacy in other age groups (e.g. in infants, study VS9_36).

8.2.1.3.1 Rationale for Combining the Menveo-Menveo and Menactra-Menveo groups

Table 8.2.1.3.1-1 shows excerpt of data from a previous study (VS9P13El) assessing the immunogenicity of a booster dose of Menveo among subjects who had previously been vaccinated with either Menveo or Menactra 3 years prior in another study (VS9P13) while subjects were 11-18 years old. The table shows almost identical seroresponse rates and 95% CIs at one-month post-booster dose of Menveo for subjects previously vaccinated with Menveo and Menactra. This suggests that data from the two groups can be pooled or combined for analysis of seroresponse following a booster dose of Menveo as planned in the current study VS9_77.

Table8.2.1.3.1-1: hSBSeroresponse at One Month Following the Booster at 3 Years After Vaccination, by Serogroup - Booster- PP Population

Vaccination	ACWY/ACWY Gtoup IV	MenactJ'a/A Group V	Difference' G1·onp IV - G1·onp V
Overall Seroresponse	68 (97%) (90-100) N=70	70(100%) (95-100) N=70	(-3%) (-10-2)
Overall Seroresponse	66 (93%) (84-98) N=71	65 (93%) (84-98) N=70	(0%) (-9-10)
Overall Seroresponse	63 (91%) (82-97) N=69	64 (93%) (84-98) N=69	(-1 %) (-11-8)
Overall Seroresponse	63 (90%) (80-96) N=70	65 (93%) (84-98) N=70	(-3%) (-13-7)

Source: [Table14.2.1.7ofClinicalStudyReportforV59PI3El](#); 'Data represented as (difference in %)(95% CI of difference).

8.2.2 Success C1iteria for Secondary Objective(s)

8.2.2.1 Success C1ite1ia for Secondar y Safety Objective(s)

There are no success criteria associated with the secondary safety objectives.

8.2.2.2 Success C1ite1ia for Secondar y Efficacy Objective(s)

There are no secondary efficacy objectives in this study.

8.2.2.3 Success Criteria for Secondary Immunogenicity Objective(s)

There are no success criteria associated with the secondary immunogenicity objectives in this study.

8.3 Analysis Sets

8.3.1 All Enrolled Set

All screened subjects who provide informed consent and provide demographic and/or baseline screening assessments, regardless of the subject's randomization and treatment status in the study, and received a Subject ID.

8.3.2 All Exposed Set

All subjects in the enrolled set who receive a study vaccination.

8.3.3 Safety Set

Solicited Safety Set (solicited local and systemic adverse events and other solicited adverse events)

All subjects in the Exposed Set with any solicited adverse event data.

Unsolicited Safety Set (unsolicited adverse events)

All subjects in the Exposed Set with unsolicited adverse event data.

Overall Safety Set

All subjects who are in the Solicited Safety Set and/or Unsolicited Safety Set.

Subjects will be analyzed as "treated" (i.e., according to the vaccine a subject received, rather than the vaccine to which the subject may have been randomized).

8.3.4 Full Analysis Set (FAS) Efficacy/Immunogenicity Set

Full Analysis Set Immunogenicity

FAS <Day 1)

All subjects in the All Enrolled Set who:

- are randomized;

- provide evaluable serum samples at Day 1 whose result is available for at least one serogroup.

FAS (Day4)

All subjects in the All Enrolled Set who:

- are randomized;
- receive the study vaccination;
- provide evaluable serum samples at Day 1 whose result is available for at least one serogroup (except for hSBA titer 8, GMTs and between-group GMRs calculated at specific timepoints); and
- provide evaluable serum samples at Day 4 whose result is available for at least one serogroup.

FAS(Day6)

All subjects in the All Enrolled Set who:

- are randomized;
- receive the study vaccination;
- provide evaluable serum samples at Day 1 whose result is available for at least one serogroup (except for hSBA titer 8, GMTs and between-group GMRs calculated at specific timepoints);
- provide evaluable serum samples at Day 6 whose result is available for at least one serogroup.

FAS (Day29)

All subjects in the All Enrolled Set who:

- are randomized;
- receive the study vaccination;
- provide evaluable serum samples at Day 1 whose result is available for at least one serogroup (except for hSBA titer 8, GMTs and between-group GMRs calculated at specific timepoints);
- provide evaluable serum samples at Day 29 whose result is available for at least one serogroup.

In case of vaccination error, subjects in the FAS sets will be analyzed "as randomized" (i.e., according to the vaccine a subject was designated to receive, which may be different from the vaccine the subject actually received).

8.3.S Per Protocol (PP) Set Efficacy/Immunogenicity Set

A PPS will be defined for each FAS described in the previous Section with additional criteria specified below: All subjects in the FAS Immunogenicity who:

- Correctly receive the study vaccine (i.e., receive the vaccine to which the subjects is randomized and at the scheduled time points).
- Have no protocol deviations leading to exclusion (see [section 8.3.8, Protocol Deviations](#)) as defined prior to unblinding / analysis.
- Are not excluded due to other reasons defined prior to unblinding or analysis (see [section 8.3.8, Protocol Deviations](#))

Examples for subjects excluded due to other reasons than protocol deviations are:

Subjects who withdrew informed consent.

8.3.6 Other Analysis Sets

There are no other analysis sets used in this study.

8.3.7 Subgroups

Using the FAS (Day 29), the analyses of the primary objectives will be replicated by: age group; center; gender; and race.

8.3.8 Protocol Deviations

A protocol deviation is any change, divergence, or departure from the study design or procedures of a study protocol. A protocol deviation may be a reason to remove data from an analysis set at the time of analysis. CSR-reportable protocol deviations will be defined as exclusionary from the analysis according to protocol objectives and endpoints, which will be specified in the statistical analysis plan. In some cases exclusion of data may be due to a reason other than a protocol deviation, e.g. early termination.

8.4 Statistical Analysis Plan

8.4.1 Analysis of Demographic and Baseline Characteristics

Descriptive statistics (mean, standard deviation, median, minimum and maximum) for age, height and weight at enrolment will be calculated overall and by study group.

Distributions of subjects by sex and ethnic origin will be summarized overall and by study group.

8.4.2 Analysis of Primary Objective(s)

8.4.2.1 Analysis of Primary Safety Objective(s)

There are no primary safety objectives in this study.

8.4.2.2 Analysis of Primary Efficacy Objective(s)

There are no primary efficacy objectives in this study.

8.4.2.3 Analysis of Primary Immunogenicity Objective(s)

8.4.2.3.1 Statistical Hypotheses

Null hypothesis: $P_i \leq 0.80$

versus

Alternative hypothesis: $P_i > 0.80$

Where: P_i is the population seroresponse rate for the pooled Menveo-Menveo and Menactra-Menveo group; $i = 1, 2, 3, 4$ refer to serogroup A, C, W and Y respectively. The level of significance is fixed at one-sided 0.025.

8.4.2.3.2 Analysis Sets

The analysis population to be used for the primary objectives is the FAS (Month 1) Set. Analyses of primary objectives will be repeated on the PPS (Month 1) to assess robustness of results.

8.4.2.3.3 Statistical Methods

General

Missing immunogenicity values are assumed MCAR (Missing Completely At Random) and therefore may not contain information that impact the result of the analysis (i.e., not informative). Imputation methods will therefore not be used.

Overall significance level for all hypothesis tests is one-sided $\alpha = 2.5\%$.

Seroresponse (Day 29)

Seroresponse is defined as: a) post-vaccination hSBA titer ≥ 8 for subjects with a pre-vaccination hSBA titer <4 ; b) for subjects with a pre-vaccination hSBA titer ≥ 4 , an increase of at least four times the pre-vaccination hSBA.

For each ACWY serogroup, the percentage of subjects with seroresponse will be computed, along with associated two-sided 95% Clopper-Pearson CIs.

Further details of the statistical methods will be provided in the SAP.

8.4.3 Analysis of Secondary Objective(s)

8.4.3.1 Analysis of Secondary Safety Objective(s)

8.4.3.1.1 Analysis of Extent of Exposure

Subjects will be analyzed to the extent that they were exposed to study vaccines and according to the available safety data for the subject during any study period. Subjects who withdraw early or who are lost to follow-up will be removed from the summary table denominator for the time period in which they have no available safety data collected.

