8.1.2 Secondary Endpoint(s)

8.1.2.1 Secondary Safety Endpoint(s)

Safety of the study vaccine will be assessed in the Menveo-Menveo, Menactra-Menveo, Naive and the pooled (Menveo-Menveo and Menactra-Menveo) groups in terms of the frequencies (percentages) of reported adverse events including:

1. Any unsolicited AEs reported within 30 minutes after vaccination;
2. Solicited local and systemic AEs reported from Day 1 (6 hours) through Day 7 after vaccination;
3. Other indicators of reactogenicity (e.g. use of analgesics / antipyretics, body temperature) within 7 days after vaccination;
4. All unsolicited AEs reported from Day 1 through Day 29 after vaccination;

¹ Seroresponse is defined for this study as follows: For subjects with pre-vaccination titers <4, post-vaccination titers 2:16; for subjects with pre-vaccination titers 2::4, post vaccination titers at least 4 times the pre-vaccination titers.

5. Medically-attended AEs, AEs leading to withdrawal and SAEs reported from Day 1 through Day 181 (entire study period).

Adverse events will be coded using MedDRA preferred terms as applicable.

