8.4.3 Analysis of Secondary Objective(s)

8.4.3.1 Analysis of Secondary Safety Objective(s)

8.4.3.1.1 Analysis of Extent of Exposure

Subjects will be analyzed to the extent that they were exposed to study vaccines and according to the available safety data for the subject during any study period. Subjects who withdraw early or who are lost to follow-up will be removed from the summary table denominator for the time period in which they have no available safety data collected.

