8.4.3.1.6 Statistical Methods

For unsolicited adverse events, the entire study period will be divided into the following intervals: onset within 30 minutes after vaccination, onset within 28 days after vaccination; and from Day 1 through Day 181. For solicited adverse events, the solicited study period will be divided into intervals: from 6 hours through day 3; from day 4 through day 7; and from 6 hours through day 7.

No imputation methods will be used to address missing safety data.

Summary of safety will be presented using frequencies and percentages within each study group. No statistical comparisons among the study groups with respect to any of the safety parameters will be performed.

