8.4.3.1.6 StatisticalMethods

For unsolicited adverse events, the entirestudy period will be divided into the following intervals: onset ~~within~~30 minutes **after** vaccination , onset within 28 days **after** vaccination; and from Day 1 through Day 181. For solicited adverse events, the solicited study period will be divided into intervals: from 6 hours through day 3; from day 4 through day 7; and from 6 hours through day 7.

No imputation methods will be used to address missing safety data.

Snmmarif>s of safety will be presented using frequencies and percentages within each study group. No statistical comparisons among the studygroups with respect to any of the safety parameters will be performed.

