Visit Window (Days)	-5 to 1	0	2 days (-1/+1), 4 days(0/+2) after vacc	3/5 days (-1/+1) after vacc	14 days (-2/+2) after vacc	28 days (-7/+14) after vacc	90 days (-14/+14) aftel' vacc	180 days (-14/+14) after vacc
Visit Number	Pre-vaccination	1	NIA	2	3	4	5	6
Study Event	References							
Subject Diary Dispensed with Training	Section 5.2.1		X					
Subject Diary Reminder Call	Section 5.2.2			xi	xi			
Subject Diary Reviewed and Collected	Section 5.3.1						X	
Assess Unsolicited AEs	Section 7.1		X		X	X	X	
Assess SAEs	Section 7.1.4		X		X	X	X	X
Assess for medically attended AEs and AEs leading to withdrawal	Sections 7.1.4.I and 7.1.3		X		X	X	X	X
Assess relevant medications/ vaccinations	Sections 5.1.2 and 6.5	X	X		X	X	X	X

Visit Type	Clinic Visit	Clinic Visit	PhoneCall	Clinic Visit	Phone Call	Clinic Visit	Phone Call	Phone Call
Study period	Screening	Treatment	Treatment	Treatment	Treatment	Treatment	Follow - up	Follow - up
Study Day		1	3, 5	4/6	15	29	91	181
Visit Window (Days)	-5 to 1	0	2 days (-1/+1), 4 days (0/+2) after vacc	3/5 days (-1/+1) after vacc	14 days (-2/+2) after vacc	28 days (-7/+14) after vacc	90 days (-14/+14) after vacc	180 days (-14/+14) after vacc
Visit Number	Pre-vaccination	1	NIA	2	3	4	5	6
Study Event	References							
Imm unogenicity								
Serology blooddraw	Section 3.5		X"		X		X	
Study C-0mp leiron								
Procedure								
StudyTennination'	Section 5.5							X

LIST OF ABBREVIATIONS

ACIP	Advisory Committee on Immunization Practices
AE	Adverse Event
CI	Confidence Interval
CBER	Center for Biologics Evaluation and Research
CRM	Cross Reactive material
CRO	Contract Research Organization
EC	Ethics Committee
eCRF	Electronic Case Report Form
EDC	Electronic Data Capture
FAS	Full Analysis Set
FDA	Food and Drug Administration
GCP	Good Clinical Practices
GMR	Geometric Mean Ratio Geometric
GMT	Mean Titer GlaxoSmithKline
GSK	Vaccines Human Serum
hSBA	Bactericidal Assay Investigator's Brochure
IB	
ICF	Informed Consent Form
ICH	International Conference on Harmonisation of Technical Requirements for Registration of Pharmaceuticals for Human Use
IM	Intramuscular
IRB	Institutional Review Board
LSLV	Last Subject Last Visit
MedDRA	Medical Dictionary for Regulatory Activities
pp	Per Protocol
Ref.	Reference
SAE	Serious Adverse Event
SOC	System Organ Class
SOP	Standard Operating Procedure

I. BACKGROUND AND RATIONALE

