6.4. Analysis of safety

6.4.1. Analysis of safety planned in the protocol

Analyses of solicited adverse events - and other solicited reactions - and unsolicited adverse events will be performed on the relevant safety sets.

For unsolicited adverse events, the entire study period will be divided into the following intervals: onset within 30 minutes after vaccination, onset within 28 days after vaccination; and from Day 1 through Day 181. For solicited adverse events, the solicited study period will be divided into intervals: from 6 hours through day 3; from day 4 through day 7; and from 6 hours through day 7.

No imputation methods will be used to address missing safety data.

Summaries of safety will be presented using frequencies and percentages within each study group. No statistical comparisons among the study groups with respect to any of the safety parameters will be performed.

| | |
|--|------------------|
| Statistical Analysis Plan | |
| Study alias & e-track number(s): V59 77 (205352) | |
| Version: 1 | Date: 19-09-2016 |

Analysis of Solicited Local, Systemic and Other Adverse Events

All solicited adverse events will be summarized according to defined severity grading scales.

Frequencies and percentages of subjects experiencing each adverse event will be presented for each symptom severity. Summary tables showing the occurrence of any local or systemic adverse event overall and at each time point will also be presented.

Post-vaccination solicited adverse events reported from Day 1 to Day 7 will be summarized for the intervals Day 1 (6 hours) – Day 3, Days 4-7, Day 1 (6 hours) – Day 7 by maximal severity and by study group. Separate analyses will be performed for solicited AEs reported 30 minutes after vaccination. The severity of solicited local adverse events, including injection-site erythema and induration, will be categorized based on linear measurement: None (0-24 mm), Mild (25-50 mm), Moderate (51-100 mm), Severe (> 100mm).

Injection site pain and systemic reactions, including fatigue, headache, myalgia, arthralgia, chills, nausea, loss of appetite, occurring up to 7 days after each vaccination will be summarized according to “mild”, “moderate” or “severe”.

Each solicited local and systemic adverse event will also be further summarized as “none” versus “any”.

Use of antipyretics and analgesics will be summarized by frequency, by type of use (prophylactic versus treatment) and percentage of subjects reporting use.

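### The Day 1–181 percentages of medically attended AEs and SAEs count time after loss to follow-up as event-free, because the denominator rule almost never acts on that interval

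*Protocol*

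**What the plan says.** The current protocol text (8.4.3.1.1) and SAP 6.2.1 carry the same rule: "Subjects who withdraw early or who are lost to follow-up will be removed from the summary table denominator for the time period", where the period meant is one without any safety data for that subject.

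Protocol 8.4.3.1.6 and SAP 6.4.1 fix the reporting intervals for unsolicited AEs: onset within 30 minutes, then "onset within 28 days after vaccination; and from Day 1 through Day 181". No interval starts after Day 29.

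The fifth secondary safety endpoint (Protocol 8.1.2.1, SAP 4.2) is "Medically-attended AEs, AEs leading to withdrawal and SAEs reported from Day 1 through Day 181 (entire study period").

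On the summary measure, SAP 6.4.1 says "Summaries of safety will be presented using frequencies and percentages within each study group", and Protocol 8.4.3.1.6 adds "No imputation methods will be used to address missing safety data". No person-time or time-to-event estimate is planned.

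Two further places matter. SAP Table 12-1 removes a vaccinated subject from the Unsolicited Safety Set only under code 115 (period D1–D181), which requires that no unsolicited safety data at all were given after vaccination. For solicited AEs, SAP 6.4.2.2 works differently: subjects without plausible data in an interval leave that interval's denominator, and the stated reason is to avoid a downward bias.

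**The concern.** The rule is meant to keep unobserved subjects out of denominators. It works only where an interval can be empty of data for a lost subject. Day 1 through Day 181 cannot be empty for anyone who was observed after vaccination, so a subject last seen on Day 10 or Day 30 is kept as if followed to Day 181 without an event. In a crude percentage this pulls the six-month frequencies of medically attended AEs and SAEs downward.

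The SAP recognises this bias for the 7-day solicited data but gives the 180-day endpoint, where there is more time to be lost, no equivalent protection. What is at stake is the accuracy of a descriptive secondary safety endpoint, not a test.

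**Working it through.** **Step 1. Whom the rule removes.** Protocol 5.2.1 requires at least 30 minutes of observation after vaccination, including for unsolicited AEs. Anyone so observed has data inside Day 1–181. Only a code 115 subject drops out, which should be rare.

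**Step 2. The plan's own drop-out figure.** 270 / 0.90 = 300 per primed group, and 700 × 0.90 = 630 evaluable. Both reproduce. This 10% converts enrolled subjects to evaluable ones for sample size (Protocol synopsis and 8.5). It is not a loss rate to Day 181, and none is stated.

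**Step 3. Model.** Assumptions: true six-month risk p, constant hazard, a share d lost independently of events, follow-up of 180 days. With R the risk accrued before loss:

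- Expected crude percentage = (1 − d)·p + d·R
- Relative understatement = d·(1 − R/p)

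The documents give no event rate, so p = 25% is assumed. The hazard is λ = −ln(0.75)/180 per day, and −ln(0.75) = 0.2877.

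- Loss spread evenly: R = 1 − 0.25/0.2877 = 13.1%
- All loss just after Day 29: R = 1 − 0.75^(28/180) = 4.4%
- All loss just after Day 1: R = 0

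**Step 4. Results against a true 25%.**

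| Loss d | Spread evenly | Just after Day 29 | Just after Day 1 |
|---|---|---|---|
| 2% | 24.8% (1.0% low) | 24.6% (1.6% low) | 24.5% (2.0% low) |
| 10% | 23.8% (4.8% low) | 22.9% (8.2% low) | 22.5% (10% low) |

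For example, 0.90 × 25% + 0.10 × 13.1% = 23.8%, and 0.90 × 25% + 0.10 × 4.4% = 22.9%.

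The relative shortfall hardly depends on p. At 10% loss spread evenly it is 5.0% for p = 1% and 4.7% for p = 30%. With independent loss it cannot exceed d.

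**Step 5. Scale.** At p = 25% and 10% loss the shift is 1.2 to 2.5 percentage points. For n = 300 the 95% CI half-width is 1.96 × √(0.25 × 0.75 / 300) = 4.9 points. For an assumed SAE risk of 1%, 10% loss moves the figure by at most 0.1 point.

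**Step 6. The closing-call window.** With calls uniform on 166 to 194 days after vaccination and all events kept, the expected percentage is 24.99% against 25%. Early and late calls cancel.

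**The case against.** The strongest reply is that this is a reported-frequency endpoint with no hypothesis, no success criterion and, by Protocol 8.4.3.1.6, no statistical comparison between groups. Missed contact also need not mean unobserved time. Withdrawing subjects are asked to stay in safety follow-up, and subjects who fail to attend prompt at least three telephone attempts and one written attempt (Protocol 3.8). Medically attended AEs and SAEs are also sought in available medical records (Protocol 3.1). All of this stands. It limits the size and the consequences but does not give the interval a working denominator. The term for the time period is also not defined. Reading it as the reporting interval is an inference, though the natural one, and Table 12-1 supports it.

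A reader might infer more than the documents support:

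- **That the rule never acts.** Code 115 does remove a vaccinated subject with no unsolicited data at all.
- **That the plan itself implies 10% loss to Day 181.** The 10% is a sample-size allowance for evaluable immunogenicity subjects.
- **That group rates will differ spuriously by a known amount.** Groups are defined by vaccination history, so unequal loss is possible, but no loss rate by group is given.
- **That early closing calls add bias.** The window is symmetric, "180 days (-14/+14) after vacc". A shortfall (24.6% against 25%) appears only if events found in late calls are discarded, which neither document says.
- **That AEs leading to withdrawal are affected in the same way.** There the event itself ends participation and is counted, so the argument does not apply.

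**Conclusion.** The point holds for medically attended AEs and SAEs. As written, the denominator rule has almost no effect on the Day 1–181 percentages, and time after loss is treated as event-free. The expected understatement is about 1–2% relative at 2% loss and 5–10% at 10% loss, and in percentage points it is smaller than the sampling error of a single group.

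This rests on independent loss, a constant hazard and an assumed loss rate. Loss linked to events could change the size or the direction, and continued follow-up or record review would reduce it. No confirmatory conclusion is affected, but the correction is cheap and worth making.

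**What to change.** In Protocol 8.4.3.1.6 and SAP 6.4.1, report for each group the cumulative proportion with a first medically attended AE, and with a first SAE, to Day 181 by Kaplan-Meier (or events per person-time). Censor at the last contact date, which already goes on the termination CRF (Protocol 3.8 and 5.5). Keep the crude percentage beside it, and show the numbers followed to Day 91 and Day 181.

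Add a simple rule for partial onset dates. SAP 11.2 uses such dates only to classify an AE as emergent or not, which is not enough for a time-to-event estimate.

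Two simpler remedies fall short. A Day 30–181 interval is a reasonable addition, but a subject last reached at Day 91 would still count as event-free to Day 181. Dividing all observed events by completers only overcorrects: in the evenly spread case, 23.8% / 0.90 = 26.5% against a true 25%.

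The cost is a little more analysis, a date rule and slightly higher reported six-month rates. No new data are collected, and no test or sample size changes.
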